### Treatment-Emergent Suicidal Ideation Compared to Recent History

A subject will be categorized as having treatment-emergent suicidal ideation compared to recent history when there is at least one post-baseline suicidal ideation score  $> 0$  and is an increase from baseline. Subjects with missing ideation in recent history and at least one post-baseline suicidal ideation score  $> 0$  will be categorized as having treatment-emergent suicidal ideation. Lifetime scores are not considered for baseline suicidal ideation responses.

### Treatment-Emergent Serious Suicidal Ideation Compared to Recent History

A subject will be categorized as having treatment-emergent serious suicidal ideation compared to recent history if the baseline score was  $< 4$  and the post-baseline suicidal ideation score increases

to 4 or 5. Subjects with missing ideation in recent history and at least one post-baseline suicidal ideation score of 4 or 5 will be categorized as having treatment-emergent serious suicidal ideation. Lifetime scores are not considered for baseline suicidal ideation responses.

#### Emergence of Serious Suicidal Ideation Compared to Recent History

A subject will be categorized as having emergence of serious suicidal ideation compared to recent history if baseline score was 0 (no suicidal ideation) and post-baseline C-SSRS suicidal ideation score is either 4 or 5. Subjects with missing ideation in recent history and at least one post-baseline suicidal ideation score of 4 or 5 will be categorized as having emergence of serious suicidal ideation. Lifetime scores are not considered for baseline suicidal ideation responses.

#### Emergence of Suicidal Behavior Compared to all Prior History

A subject will be categorized as having emergence of suicidal behavior compared to all prior history if there had been no suicidal behavior in Categories 6-10 reported at any pre-treatment assessment, including responses to lifetime history questions, and there is at least one positive post-baseline C-SSRS assessment in Categories 6-10. Subjects with missing suicidal behavior at any pre-treatment assessment, and there is at least one post-baseline suicidal behavior score will be categorized as having emergence of suicidal behavior. ‘All Prior History’ represents lifetime history.

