#### **5.15.7. Columbia-Suicide Severity Rating Scale (C-SSRS)**

The maximum post-baseline results from the C-SSRS will be summarized. The maximum of each subscale (suicidal ideation [Categories 1-5], suicidal behavior [Categories 6-10], suicidal ideation or behavior [Categories 1-10], and self-injurious behavior without suicidal intent) will be presented. The number of patients with suicide-related treatment-emergent events, treatment-emergent suicidal ideation, and suicidal behavior, based on a comparison of the C-SSRS at baseline and/or previous lifetime experience to maximum C-SSRS scores across all post-baseline assessments will be provided for each treatment. All C-SSRS elements will be reflected in a listing.

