## 9.2. Columbia-Suicide Severity Rating Scale (C-SSRS) Suicidal Ideation and Suicidal Behavior Scores

The C-SSRS is comprised of 10 categories with binary responses. The 10 categories include:

Category 1 – Wish to be Dead

Category 2 – Non-specific Active Suicidal Thoughts

Category 3 – Active Suicidal Ideation with Any Methods (Not Plan) without Intent to Act

Category 4 – Active Suicidal Ideation with Some Intent to Act, without Specific Plan

Category 5 – Active Suicidal Ideation with Specific Plan and Intent

Category 6 – Preparatory Acts or Behavior

Category 7 – Aborted Attempt

Category 8 – Interrupted Attempt

Category 9 – Actual Attempt (non-fatal)

Category 10 – Completed Suicide

Categories 1-5 represent Suicidal Ideation and categories 6-10 represent Suicidal Behavior. Each category is scored as 1 if there is a positive response in the category and a 0 if there are no positive responses in the category.

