### Baseline C-SSRS Score

Baseline represents the pre-treatment assessment of recent history, with elements of suicidal ideation assessed over the prior 6 months and elements of suicidal behavior assessed over the prior 2 years. It is scaled from 0 (no suicidal ideation or behavior) to 10 (completed suicide).

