### Treatment-Emergent Suicide-Related Event

A subject will be categorized as having a treatment-emergent suicide-related event if at least one post-baseline suicidal ideation or suicidal behavior score is greater than 0.

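### The SAP's missing-history rule for emergent suicidal behavior omits the positive-response threshold, so as written a participant with only zero scores after baseline can be counted as a case

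*SAP*

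**What the plan says.** SAP Section 9.2 defines the derived C-SSRS categories. Categories 1-5 are ideation and 6-10 are behavior. The definition headed Emergence of Suicidal Behavior Compared to all Prior History has two parts.

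- **Main rule.** No behavior is on record before treatment, lifetime questions included, and "there is at least one positive post-baseline C-SSRS assessment in Categories 6-10".
- **Missing-history rule.** "Subjects with missing suicidal behavior at any pre-treatment assessment, and there is at least one post-baseline suicidal behavior score will be categorized" as having emergence. No level is attached to the score.

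The section states the scoring twice. At category level: "Each category is scored as 1 if there is a positive response in the category and a 0 if there are no positive responses". For the baseline score: "It is scaled from 0 (no suicidal ideation or behavior) to 10 (completed suicide").

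The other definitions in Section 9.2 state a level. A treatment-emergent suicide-related event needs that "at least one post-baseline suicidal ideation or suicidal behavior score is greater than 0". The missing-history rule for ideation begins "Subjects with missing ideation in recent history and at least one post-baseline suicidal ideation score" and continues with a threshold above 0. For serious ideation it reads "Subjects with missing ideation in recent history and at least one post-baseline suicidal ideation score of 4 or 5 will be categorized", and the rule for emergence of serious ideation uses the same 4-or-5 threshold.

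SAP Section 5.15.7 reports the resulting counts for each treatment, "based on a comparison of the C-SSRS at baseline and/or previous lifetime experience to maximum C-SSRS scores across all post-baseline assessments".

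**The concern.** The two sentences of one definition set different conditions for the same label. With a complete, negative history, a participant must show suicidal behavior after baseline to be counted. With a missing history, the text asks only that a post-baseline score exist. Any participant who has a missing pre-treatment behavior response and completes a later C-SSRS meets that condition, even if every later answer is negative.

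The trigger is also loosely worded. Two pre-treatment forms are planned, one at Screening and one at Baseline (protocol Section 1.3, footnote r). If missing behavior at *any* of them means at one or more, the rule also applies to someone whose lifetime history was recorded at Screening and whose Day 1 form is absent. Such people can be enrolled, because Exclusion Criterion 10 bars suicidal behavior only within the past 2 years.

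What is at stake is the accuracy of one row in a safety table. Clinically significant C-SSRS findings are a listed endpoint under the secondary objective, and the entry criteria screen out recent suicidal behavior and serious suicide risk. True counts may therefore be small, and a small count is easily distorted by a few misclassified participants.

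**Working it through.** The documents state no figure on this point, so there is nothing to reproduce. The check is one of logic, followed by an illustration of size.

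**Step 1: can a suicidal behavior score be 0?** Yes. Section 9.2 assigns 0 to a category with no positive response and starts the baseline scale at 0. The suicide-related event definition tests whether a behavior score exceeds 0, which would be redundant if every score were positive.

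**Step 2: apply the rule as written, then with a positive response required.**

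| Pre-treatment behavior | Highest post-baseline behavior response | As written | Positive response required |
|---|---|---|---|
| None on record | 0 | Not emergent | Not emergent |
| None on record | Positive | Emergent | Emergent |
| On record, no form missing | 0 | Not emergent | Not emergent |
| On record, no form missing | Positive | Not emergent | Not emergent |
| Missing | 0 | **Emergent** | Not emergent |
| Missing | Positive | Emergent | Emergent |

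Only the fifth row changes. Missing history with a positive response still counts, so the conservative handling of missing history is kept.

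**Step 3: the trigger.** Take a participant with a lifetime attempt recorded at Screening, no Day 1 form, and a positive post-baseline response.

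- The main rule does not count this participant, because behavior is on record.
- The missing-history rule does, if *any* means one or more.

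The two sentences then give opposite answers, and adding the threshold does not settle it. This participant did have suicidal behavior on treatment. What is wrong is the label of new against all prior history.

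**Step 4: possible size of the first gap.** The documents give no rate of missing pre-treatment behavior data, so the rate *m* is an assumption, shown over a range that includes 0. The arm size of 124 and the total of 372 are the planned numbers (SAP Section 1.1). Assume also that every affected participant has at least one post-baseline C-SSRS, that all those scores are 0, and that missingness is independent between participants.

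- Expected false cases per arm = 124 × *m*; in the trial = 372 × *m*
- Chance of at least one in an arm = 1 − (1 − *m*)^124

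| Assumed *m* | Expected per arm | Expected in trial | Chance of at least one in an arm |
|---|---|---|---|
| 0% | 0 | 0 | 0% |
| 0.5% | 124 × 0.005 = 0.62 | 1.86 | 46% |
| 1% | 124 × 0.01 = 1.24 | 3.72 | 71% |
| 2% | 124 × 0.02 = 2.48 | 7.44 | 92% |
| 5% | 124 × 0.05 = 6.20 | 18.6 | 99.8% |

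**The case against.** The best reply is that no one would program it this way. The sentence before says positive, the heading is about emergence of behavior, and Section 5.15.7 bases the counts on a comparison with the highest post-baseline score. A maximum of 0 cannot sensibly be emergence. The SAP nowhere says that zeros count; that follows only from its own definition of a score. All of this stands as evidence of intent, and the gap is most likely a slip. But Section 9.2 is the derivation text, and here it gives the wrong answer. Independent programming (SAP Section 9.4) is weak protection when both programmers read the same sentence.

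A second reply is that the situation should hardly arise. The Screening C-SSRS decides eligibility, the Baseline form confirms it, all screening evaluations must be reviewed, and participants are inpatients from consent. This stands, and it is why the range above starts at 0.

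A third reply is that an error would show. Section 5.15.7 also summarizes the maximum post-baseline behavior and lists all C-SSRS elements, so a false case with all-zero follow-up would contradict both. That helps detection. A correction made then would, however, be a departure from the SAP, to be documented under its Section 6.

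**Conclusion.** The rule is wrong as written. The missing-history sentence lacks the threshold that the main rule and the parallel ideation rules carry, and followed literally it counts participants with no post-baseline suicidal behavior. Its trigger can also conflict with a recorded lifetime history.

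The effect is confined to a descriptive safety count; the primary analysis, alpha and sample size are untouched. The number of false cases could be 0, and is about 1 per arm at an assumed 1% missing.

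Three stronger conclusions that a reader might draw are not supported.

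- *False cases would outnumber true ones.* The documents give neither a missing rate nor an expected rate of suicidal behavior, and eligibility-driven collection makes near-zero missingness plausible.
- *The rule would produce a treatment-related imbalance.* The missing data are pre-treatment: Screening precedes randomization, Baseline assessments precede dosing, and the trial is double-blind. Any imbalance would be chance.
- *The loose trigger creates false suicidality events.* Once a positive response is required, it affects only participants with a real post-baseline positive. It mislabels that behavior as new, and only if *any* is read as one or more.

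**What to change.** Replace the missing-history sentence in SAP Section 9.2 with:

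*Subjects with no positive response in Categories 6-10 at any available pre-treatment assessment (lifetime history included), among them those whose pre-treatment responses are all missing, who have at least one positive post-baseline response in Categories 6-10 are counted as emergence of suicidal behavior; subjects with a positive response at any pre-treatment assessment are not.*

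This closes both gaps. The cost is one sentence in the SAP and one line in the derivation program, with no change to data collection.

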### 9.3. CTCAE Based Laboratory Test Results Grading Specifications

**Lab Test = Albumin**

CTCAE Term	Grade 1	Grade 2	Grade 3	Grade 4	Grade 5
Hypoalbuminemia	<LLN - 3 g/dL; <LLN - 30 g/L	<3 - 2 g/dL; <30 - 20 g/L	<2 g/dL; <20 g/L	Life-threatening consequences; urgent intervention indicated	Death

Albumin will have grades 1-3,

- Grade 1 being any values from the LLN to 3 g/dL,
- Grade 2 from 2 to < 3 g/dL and
- Grade 3 < 2 g/dL

**Lab Test = Amylase**

CTCAE Term	Grade 1	Grade 2	Grade 3	Grade 4	Grade 5
Serum amylase increased	>ULN - 1.5 x ULN	>1.5 - 2.0 x ULN; >2.0 - 5.0 x ULN and asymptomatic	>2.0 - 5.0 x ULN with signs or symptoms; >5.0 x ULN and asymptomatic	>5.0 x ULN and with signs or symptoms	-

Amylase will have Grades 1, 2 and 3:

- Grade 1 being any values from the ULN to 1.5 x ULN
- Grade 2 from >1.5 to 5.0 x ULN
- Grade 3 from >5 x ULN

**Lab Test = Alkaline Phosphatase**

CTCAE Term	Grade 1	Grade 2	Grade 3	Grade 4	Grade 5
Alkaline phosphatase increased	>ULN - 2.5 x ULN if baseline was normal; 2.0 - 2.5 x baseline if baseline was abnormal	>2.5 - 5.0 x ULN if baseline was normal; >2.5 - 5.0 x baseline if baseline was abnormal	>5.0 - 20.0 x ULN if baseline was normal; >5.0 - 20.0 x baseline if baseline was abnormal	>20.0 x ULN if baseline was normal; >20.0 x baseline if baseline was abnormal	-

Alkaline Phosphatase will have grades 1-4 and grading is based ULN only.

- Grade 1 being any values from the ULN to 2.5 x ULN
- Grade 2 from >2.5 to 5.0 x ULN
- Grade 3 from >5.0 to 20.0 x ULN
- Grade 4 from >20.0 x ULN

**Lab Test = Alanine Aminotransferase**

CTCAE Term	Grade 1	Grade 2	Grade 3	Grade 4	Grade 5
Alanine aminotransferase increased	>ULN - 3.0 x ULN if baseline was normal; 1.5 - 3.0 x baseline if baseline was abnormal	>3.0 - 5.0 x ULN if baseline was normal; >3.0 - 5.0 x baseline if baseline was abnormal	>5.0 - 20.0 x ULN if baseline was normal; >5.0 - 20.0 x baseline if baseline was abnormal	>20.0 x ULN if baseline was normal; >20.0 x baseline if baseline was abnormal	-

ALT will have grades 1-4 and grading is based ULN only. The baseline abnormality will be ignored.

- Grade 1 being any values from the ULN to 3.0 x ULN
- Grade 2 from >3.0 to 5.0 x ULN
- Grade 3 from >5.0 to 20.0 x ULN
- Grade 4 from >20.0 x ULN

**Lab Test = Aspartate Aminotransferase**

CTCAE Term	Grade 1	Grade 2	Grade 3	Grade 4	Grade 5
Aspartate aminotransferase increased	>ULN - 3.0 x ULN if baseline was normal; 1.5 - 3.0 x baseline if baseline was abnormal	>3.0 - 5.0 x ULN if baseline was normal; >3.0 - 5.0 x baseline if baseline was abnormal	>5.0 - 20.0 x ULN if baseline was normal; >5.0 - 20.0 x baseline if baseline was abnormal	>20.0 x ULN if baseline was normal; >20.0 x baseline if baseline was abnormal	-

AST will have grades 1-4 and grading is based ULN only.

- Grade 1 being any values from the ULN to 3.0 x ULN
- Grade 2 from >3.0 to 5.0 x ULN
- Grade 3 from >5.0 to 20.0 x ULN
- Grade 4 from >20.0 x ULN

**Lab Test = Bilirubin**

CTCAE Term	Grade 1	Grade 2	Grade 3	Grade 4	Grade 5
Blood bilirubin increased	>ULN - 1.5 x ULN if baseline was normal; >1.0 - 1.5 x baseline if baseline was abnormal	>1.5 - 3.0 x ULN if baseline was normal; >1.5 - 3.0 x baseline if baseline was abnormal	>3.0 - 10.0 x ULN if baseline was normal; >3.0 - 10.0 x baseline if baseline was abnormal	>10.0 x ULN if baseline was normal; >10.0 x baseline if baseline was abnormal	-

Bilirubin will have grades 1-4 and grading is based ULN only

- Grade 1 being any values from the ULN to 1.5 x ULN
- Grade 2 from >1.5 to 3.0 x ULN
- Grade 3 from >3.0 to 10.0 x ULN
- Grade 4 from >10.0 x ULN

**Lab Test = Corrected Serum Calcium**

CTCAE Term	Grade 1	Grade 2	Grade 3	Grade 4	Grade 5
Hypocalcemia	Corrected serum calcium of <LLN - 8.0 mg/dL; <LLN - 2.0 mmol/L; Ionized calcium <LLN - 1.0 mmol/L	Corrected serum calcium of <8.0 - 7.0 mg/dL; <2.0 - 1.75 mmol/L; Ionized calcium <1.0 - 0.9 mmol/L; symptomatic	Corrected serum calcium of <7.0 - 6.0 mg/dL; <1.75 - 1.5 mmol/L; Ionized calcium <0.9 - 0.8 mmol/L; hospitalization indicated	Corrected serum calcium of <6.0 mg/dL; <1.5 mmol/L; Ionized calcium <0.8 mmol/L; life-threatening consequences	Death
Hypercalcemia	Corrected serum calcium of >ULN - 11.5 mg/dL; >ULN - 2.9 mmol/L; Ionized calcium >ULN - 1.5 mmol/L	Corrected serum calcium of >11.5 - 12.5 mg/dL; >2.9 - 3.1 mmol/L; Ionized calcium >1.5 - 1.6 mmol/L; symptomatic	Corrected serum calcium of >12.5 - 13.5 mg/dL; >3.1 - 3.4 mmol/L; Ionized calcium >1.6 - 1.8 mmol/L; hospitalization indicated	Corrected serum calcium of >13.5 mg/dL; >3.4 mmol/L; Ionized calcium >1.8 mmol/L; life-threatening consequences	Death

Calcium will have to be corrected for albumin using the formula previously discussed (NOTE: It should be confirmed with the lab whether or not the correction has already been applied). The grading is in both directions High and Low. Both directions are graded in 4 categories as Hypercalcemia

- Grade 1 being any values from the ULN to 11.5 mg/dL,
- Grade 2 from >11.5 to 12.5 mg/dL,
- Grade 3 from >12.5 to 13.5 mg/dL,
- Grade 4 >13.5 mg/dL

**Hypocalcemia**

- Grade 1 being any values from the LLN to 8.0 mg/dL,
- Grade 2 from 7.0 to <8.0 mg/dL,
- Grade 3 from 6.0 to <7.0 mg/dL,
- Grade 4 <6.0 mg/dL

**Lab Test = Cholesterol**

CTCAE Term	Grade 1	Grade 2	Grade 3	Grade 4	Grade 5
Cholesterol high	>ULN - 300 mg/dL; >ULN - 7.75 mmol/L	>300 - 400 mg/dL; >7.75 - 10.34 mmol/L	>400 - 500 mg/dL; >10.34 - 12.92 mmol/L	>500 mg/dL; >12.92 mmol/L	-

Cholesterol will have grades 1-4,

- Grade 1 being any values from the ULN to 300 mg/dL,
- Grade 2 from >300 to 400 mg/dL,
- Grade 3 from >400 to 500 mg/dL,
- Grade 4 >500 mg/dL

**Lab Test = Creatine Kinase**

CTCAE Term	Grade 1	Grade 2	Grade 3	Grade 4	Grade 5
CPK increased	>ULN - 2.5 x ULN	>2.5 x ULN - 5 x ULN	>5 x ULN - 10 x ULN	>10 x ULN	-

Creatine Kinase will have grades 1-4,

- Grade 1 being any values from the ULN to 2.5 x ULN,
- Grade 2 from >2.5 to 5 x ULN,
- Grade 3 from >5 to 10 x ULN,
- Grade 4 >10 ULN

**Lab Test = Creatinine**

CTCAE Term	Grade 1	Grade 2	Grade 3	Grade 4	Grade 5
Creatinine increased	>ULN - 1.5 x ULN	>1.5 - 3.0 x baseline; >1.5 - 3.0 x ULN	>3.0 x baseline; >3.0 - 6.0 x ULN	>6.0 x ULN	-

Creatinine will have grades 1-4 and will be based on the baseline value in some cases. Grading for pre-baseline values will ignore the baseline requirement.

- Grade 1 being any values from the ULN to 1.5 x ULN,
- Grade 2 from >1.5 to 3.0 x ULN or >1.5 - 3.0 x baseline,
- Grade 3 from >3.0 to 6.0 x ULN or >3.0 x baseline,
- Grade 4 >6.0 x ULN

**Lab Test = Fibrinogen**

CTCAE Term	Grade 1	Grade 2	Grade 3	Grade 4	Grade 5
Fibrinogen decreased	<1.0 - 0.75 x LLN; if abnormal, <25% decrease from baseline	<0.75 - 0.5 x LLN; if abnormal, 25 - <50% decrease from baseline	<0.5 - 0.25 x LLN; if abnormal, 50 - <75% decrease from baseline	<0.25 x LLN; if abnormal, 75% decrease from baseline; absolute value <50 mg/dL	-

Fibrinogen will have Grades 1- 4:

- Grade 1  $<1.0 - 0.75 \times LLN$
- Grade 2  $<0.75 - 0.5 \times LLN$
- Grade 3  $<0.5 - 0.25 \times LLN$
- Grade 4  $<0.25 \times LLN$

**Lab Test = Gamma-Glutamyl Transpeptidase**

CTCAE Term	Grade 1	Grade 2	Grade 3	Grade 4	Grade 5
GGT increased	>ULN - 2.5 x ULN if baseline was normal; 2.0 - 2.5 x baseline if baseline was abnormal	>2.5 - 5.0 x ULN if baseline was normal; >2.5 - 5.0 x baseline if baseline was abnormal	>5.0 - 20.0 x ULN if baseline was normal; >5.0 - 20.0 x baseline if baseline was abnormal	>20.0 x ULN if baseline was normal; >20.0 x baseline if baseline was abnormal	-

Gamma-Glutamyl Transpeptidase will have grades 1-4 and based on ULN only

- Grade 1 being any values from the ULN to  $2.5 \times ULN$ ,
- Grade 2 from  $>2.5$  to  $5.0 \times ULN$
- Grade 3 from  $>5.0$  to  $20.0 \times ULN$
- Grade 4 from  $>20.0 \times ULN$

**Lab Test = Glucose**

CTCAE Term	Grade 1	Grade 2	Grade 3	Grade 4	Grade 5
Hyperglycemia	Abnormal glucose above baseline with no medical intervention	Change in daily management from baseline for a diabetic; oral antiglycemic agent initiated; workup for diabetes	Insulin therapy initiated; hospitalization indicated	Life-threatening consequences; urgent intervention indicated	Death
Hypoglycemia	<LLN - 55 mg/dL; <LLN - 3.0 mmol/L	<55 - 40 mg/dL; <3.0 - 2.2 mmol/L	<40 - 30 mg/dL; <2.2 - 1.7 mmol/L	<30 mg/dL; <1.7 mmol/L; life-threatening consequences; seizures	Death

Glucose is graded in 2 directions.

Hypoglycemia will have grades 1-4,

- Grade 1 being any values from the LLN to 55 mg/dL,
- Grade 2 from 40 to <55 mg/dL,
- Grade 3 from 30 to <40 mg/dL,
- Grade 4 <30 mg/dL

Hyperglycemia will have one grade. We discussed using the WHO criterion as noted below

- Grade 1 >200 mg/dL;

**Lab Test = Lipase**

CTCAE Term	Grade 1	Grade 2	Grade 3	Grade 4	Grade 5
Serum lipase increased	>ULN - 1.5 x ULN	>1.5 - 2.0 x ULN; >2.0 - 5.0 x ULN and asymptomatic	>2.0 - 5.0 x ULN with signs or symptoms; >5.0 x ULN and asymptomatic	>5.0 x ULN and with signs or symptoms	-

Lipase will have Grades 1, 2 and 3:

- Grade 1 being any values from the ULN to 1.5 x ULN
- Grade 2 from >1.5 to 5.0 x ULN
- Grade 3 from >5 x ULN

**Lab Test = Magnesium**

CTCAE Term	Grade 1	Grade 2	Grade 3	Grade 4	Grade 5
Hypermagnesemia	>ULN - 3.0 mg/dL; >ULN - 1.23 mmol/L	-	>3.0 - 8.0 mg/dL; >1.23 - 3.30 mmol/L	>8.0 mg/dL; >3.30 mmol/L; life-threatening consequences	Death
Hypomagnesemia	<LLN - 1.2 mg/dL; <LLN - 0.5 mmol/L	<1.2 - 0.9 mg/dL; <0.5 - 0.4 mmol/L	<0.9 - 0.7 mg/dL; <0.4 - 0.3 mmol/L	<0.7 mg/dL; <0.3 mmol/L; life-threatening consequences	Death

Hypermagnesemia will have grades 1, 3, and 4,

- Grade 1 being any values from the ULN to 3.0 mg/dL,
- Grade 3 from >3.0 to 8.0 mg/dL,
- Grade 4 from >8.0 mg/dL

Hypomagnesemia will have grades 1 - 4,

- Grade 1 being any values from the LLN to 1.2 mg/dL,
- Grade 2 from 0.9 to <1.2 mg/dL,
- Grade 3 from 0.7 to <0.9 mg/dL,
- Grade 4 <0.7 mg/dL

**Lab Test = Potassium**

CTCAE Term	Grade 1	Grade 2	Grade 3	Grade 4	Grade 5
Hyperkalemia	>ULN - 5.5 mmol/L	>5.5 - 6.0 mmol/L; intervention initiated	>6.0 - 7.0 mmol/L; hospitalization indicated	>7.0 mmol/L; life-threatening consequences	Death
Hypokalemia	<LLN - 3.0 mmol/L	Symptomatic with <LLN - 3.0 mmol/L; intervention indicated	<3.0 - 2.5 mmol/L; hospitalization indicated	<2.5 mmol/L; life-threatening consequences	Death

Hyperkalemia will have grades 1-4,

- Grade 1 being any values from the ULN to 5.5 mmol/L,
- Grade 2 from >5.5 to 6.0 mmol/L,
- Grade 3 from >6.0 to 7.0 mmol/L,
- Grade 4 from >7.0 mmol/L

Hypokalemia will have grades 1, 3, and 4,

- Grade 1 being any values from the LLN to 3.0 mmol/L,
- Grade 3 from >2.5 to 3.0 mmol/L,
- Grade 4 <2.5 mmol/L

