### **5.15.3. Clinical Laboratory Assessments**

Descriptive summaries of selective (quantitative) clinical laboratory results and change from baseline will be presented by study visit. Additionally, for hematology, blood chemistry, coagulation, and urinalysis parameters, toxicity grade will be determined for laboratory tests with toxicity grade specified in [Section 9.3](#). Shifts from baseline to greatest (worst) post-baseline laboratory grade will be presented. For parameters not graded as described above, laboratory values outside the normal range for each systematically collected hematology, blood chemistry, and urinalysis parameters defined in Protocol Section 10.2 will be identified using shift tables. Each subject's hematology, blood chemistry, and quantitative urinalysis values will be flagged as "low" (below the lower limit of normal/LLN), "normal" (within the normal range), or "high" (above the upper limit of normal/ULN) relative to the normal ranges of the central laboratory. Each subject's qualitative urinalysis values will be flagged as "normal" or "abnormal". Shifts from baseline to high/normal/low status for the hematology, blood chemistry, and urinalysis parameters will be presented to for the maximum post-baseline value and the minimum

post-baseline value for each laboratory test. Shifts from baseline to normal/abnormal status for urinalysis parameters will be presented to the maximum post-baseline value and the minimum post-baseline value for each laboratory test.

The number and percentage of subjects who have post-baseline elevations in transaminases (alanine aminotransferase [ALT] or aspartate aminotransferase [AST]) or bilirubin abnormalities in relation to fold above the upper limit of normal will be summarized according to the Food and Drug Administration's Premarketing Clinical Evaluation on Drug-Induced Liver Injury Guidance for Industry ([FDA 2009](#)). Abnormal hepatic laboratory values will be categorized and evaluated for any occurrence among all post-baseline assessments. [REDACTED]

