**Lab Test = Triglycerides**

CTCAE Term	Grade 1	Grade 2	Grade 3	Grade 4	Grade 5
Hypertriglyceridemia	150 mg/dL - 300 mg/dL; 1.71 mmol/L - 3.42 mmol/L	>300 mg/dL - 500 mg/dL; >3.42 mmol/L - 5.7 mmol/L	>500 mg/dL - 1000 mg/dL; >5.7 mmol/L - 11.4 mmol/L	>1000 mg/dL; >11.4 mmol/L; life-threatening consequences	Death

Triglycerides will have grades 1-4,

- Grade 1 being any values from the 150 to 300 mg/dL,
- Grade 2 from >300 to 500 mg/dL,
- Grade 3 from >500 to 1000 mg/dL,
- Grade 4 from >1000 mmol/L

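### The SAP 9.3 grading bullets for hypokalemia and triglycerides contradict the CTCAE rows above them, so some results meet two grades or none

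*SAP*

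**What the plan says.** SAP 5.15.3 takes toxicity grades from Section 9.3 and uses them in a shift table: "Shifts from baseline to greatest (worst) post-baseline laboratory grade will be presented". Section 9.3 gives each test a CTCAE row and, below it, bullets with the numerical cut-offs.

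**Potassium, low direction.** The bullets are "Grade 1 being any values from the LLN to 3.0 mmol/L", then "Grade 3 from >2.5 to 3.0 mmol/L", then "Grade 4 <2.5 mmol/L". The row above them defines Grade 3 as "<3.0 - 2.5 mmol/L; hospitalization indicated". The row's Grade 2 has the same numerical range as Grade 1 and depends on symptoms or intervention, and the bullets omit it. On numbers alone, both versions therefore use Grades 1, 3 and 4.

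**Triglycerides.** The bullets for Grades 1 to 3 are in mg/dL and end with "Grade 3 from >500 to 1000 mg/dL". The next bullet is "Grade 4 from >1000 mmol/L". The row gives Grade 4 as ">1000 mg/dL; >11.4 mmol/L; life-threatening consequences".

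**The concern.** A grading specification should give every abnormal result exactly one grade. These bullets do not, and they differ from the rows directly above them. No other part of the SAP or protocol corrects them.

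A programmer cannot simply fall back on the row. Elsewhere in Section 9.3 the bullets depart from the rows on purpose: ALT is graded without regard to an abnormal baseline, hyperglycemia is reduced to one grade above 200 mg/dL, and high WBC gets a Grade 1 above 11,000/mm³ that the row does not contain. A reader would reasonably take the bullets as the working rules here too.

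Potassium and triglycerides are both required safety tests (Protocol Table 7). After baseline, the Schedule of Assessments plans safety blood only at Week 3 and at Week 6 or early termination, so a single ungraded result can decide a participant's cell in the shift table. SAP 5.15.3 reserves the low/normal/high shift tables for parameters that are not graded, so they are not designed to pick up an ungraded result of a graded test.

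**Working it through.** No stated figure has to be reproduced. The check applies the bullets and the rows to the same values.

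**Potassium.** The bullets, as intervals in mmol/L:

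- Grade 1: 3.0 ≤ K < LLN
- Grade 3: 2.5 < K ≤ 3.0
- Grade 4: K < 2.5

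The row, as intervals:

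- Grade 1: 3.0 ≤ K < LLN
- Grade 3: 2.5 ≤ K < 3.0
- Grade 4: K < 2.5

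The documents give no LLN and no reporting precision. I assumed an LLN of 3.5 and steps of 0.1 mmol/L, and tested 2.0 to 3.5.

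| Potassium (mmol/L) | Bullets | Row |
|---|---|---|
| 2.0 to 2.4 | 4 | 4 |
| 2.5 | none | 3 |
| 2.6 to 2.9 | 3 | 3 |
| 3.0 | 1 and 3 | 1 |
| 3.1 to 3.4 | 1 | 1 |

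Only 2.5 and 3.0 disagree, and the result is the same for an LLN of 3.3, 3.4, 3.5 or 3.6. The cause is that Grade 3 excludes its lower end and includes its upper end. The bullets for the other low-direction chemistry tests do the reverse: sodium Grade 3 is 120 to below 125 mmol/L, magnesium 0.7 to below 0.9 mg/dL, glucose 30 to below 40 mg/dL and calcium 6.0 to below 7.0 mg/dL.

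**Triglycerides.** The row gives each cut-off in both units, which fixes the conversion:

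- 150 / 1.71 = 300 / 3.42 = 500 / 5.7 = 1000 / 11.4 = 87.72 mg/dL per mmol/L

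The Grade 4 bullet read literally is therefore

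- 1000 mmol/L × (1000 / 11.4) = 87,719 mg/dL, which is 87.7 times the row's 1000 mg/dL.

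| Triglycerides (mg/dL) | Bullets, literal | Row |
|---|---|---|
| 501 | 3 | 3 |
| 1000 | 3 | 3 |
| 1001 | none | 4 |
| 1500 | none | 4 |
| 5000 | none | 4 |
| 87,719 | none | 4 |
| 87,720 | 4 | 4 |

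Grade 3 stops at 1000 mg/dL, so values above it are not moved to a lower grade. They have no grade until about 87,719 mg/dL.

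**After correction.** With the bullets set to the rows, 3.0 is Grade 1 only, 2.5 is Grade 3, every potassium below LLN has exactly one grade, and every triglyceride above 1000 mg/dL is Grade 4.

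**The case against.** Several points on the other side are fair.

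- A reader might infer that the worst-grade rule turns a potassium of 3.0 into Grade 3. It does not. That rule selects among a participant's post-baseline results and does not say how to grade one result that meets two definitions. The outcome depends on how the program orders its conditions, so the result could be graded 1 or 3.
- No general order of precedence between rows and bullets is stated, and for eGFR the SAP refers back to the CTCAE values. Treating the bullets as the rules is a reasonable inference, not a stated rule. The missing precedence is itself a reason to reconcile the two.
- The triglyceride bullet looks like a unit slip: Grades 1 to 3 are in mg/dL and the row above is clear. A programmer may well notice, and SAP 9.4 requires independent programming and verification by the lead statistician. A reader might infer that Grade 4 can never be assigned, or that the cut-off is physiologically unreachable. The first holds only if the line is coded literally, and the documents give no physiological maximum. The factor of 87.7 measures the slip, not its effect on results.
- Most affected triglyceride values would still be counted elsewhere. SAP 5.15.3 separately counts rises of at least 50 mg/dL and shifts from normal or borderline to at least 200 mg/dL. That summary has no category above 1000 mg/dL, so it does not replace the grade.

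These points limit the consequence. They do not remove the contradiction, and verification against a faulty specification can reproduce the fault.

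**Conclusion.** The bullets and rows in SAP 9.3 contradict each other for hypokalemia and triglycerides. Potassium of exactly 3.0 mmol/L could be graded 1 or 3, exactly 2.5 has no grade, and triglycerides just above 1000 mg/dL have no grade if the bullet is coded literally.

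This is a minor drafting fault. It reaches only the worst-grade shift tables, and an ungraded value matters there only when it is the one that should set the participant's worst grade. Few participants are likely to be affected, although the documents give no frequencies from which to count them. The potassium part rests on the assumption that results can fall exactly on 3.0 or 2.5; the triglyceride part rests on literal coding. The efficacy analyses, alpha and power are unaffected.

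**What to change.** Change the bullets in SAP 9.3 to agree with the rows already printed there:

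- Hypokalemia Grade 1: below LLN to 3.0 mmol/L; Grade 3: 2.5 to below 3.0 mmol/L; Grade 4: below 2.5 mmol/L.
- Triglycerides Grade 4: above 1000 mg/dL (above 11.4 mmol/L).

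In substance two lines change, the hypokalemia Grade 3 bullet and the triglyceride Grade 4 bullet. The change concerns how results are graded for tabulation only. It needs no new data and no change to trial conduct, and it costs almost nothing if made before the tables are programmed.
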